COVER LETTER

**Title: Cardio-pulmonary Rehabilitation and
Sleep Quality**

NCT Number: NCT04668599

Document Date: 05/10/2020

STATISTICAL ANALYSIS PLAN

Statistical Analysis Plan Data will be analyzed using SPSS and STATA. The primary outcome measure will be the change in individual Pittsburgh sleep quality index scores at the beginning, end and after 3-months of cardiac and pulmonary rehabilitation. Secondary outcome measures will include changes in the hospital anxiety and depression scale, insomnia severity index, COPD assessment test, Epworth sleepiness scale, short form survey36, insomnia severity index at the beginning, end and after 3-months of cardiac and pulmonary rehabilitation. A paired-sample Student t-test will be used to compare means before and after the CP-R. Pearson's product co-efficient (r) will be used to analyze association between changes in Pittsburgh sleep quality index, hospital anxiety and depression scale, COPD assessment test, Epworth sleepiness scale, Short form health survey-36 at the beginning, in the CP-R cohort. We are planning a study of a continuous response variable from matched pairs of study subjects. Prior data indicate that the difference in the response of matched pairs is normally distributed with standard deviation 4.6. If the true difference in the mean response of matched pairs is 3, we will need to study 27 pairs of subjects to be able to reject the null hypothesis that this response difference is zero with probability (power) 0.9 (90%). The Type I error probability associated with this test of this null hypothesis is 0.05.

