This is your abstract also known as a synopsis from an industry sponsored study. Please limit to 500 words.

Goals and objectives:

The purposes of this study are to:

- 1) Evaluate the effect of CP-R on sleep quality in patients with chronic lung and heart diseases.
- 2) Determine the longevity of sleep quality improvement by conducting a follow-up survey
- 3) Determine if sleep quality impairment correlates with positive screen for sleep apnea.

7.2 * What are the specific aims of this study i.e. what are the question(s) this research intends to answer? Provide at a maximum 3 primary and 3 secondary aims.

Primary aims:

1. Does cardiac-pulmonary rehabilitation (CP-R) lead to improved sleep quality?
2. Does the improvement in sleep quality persist after 3 months?
3. Is sleep impairment associated with positive screen for sleep apnea?

Secondary aims:

1. Does the improvement in sleep quality correlates with improvement in excessive daytime sleepiness, health related quality of life as determined by COPD assessment test score for COPD patients, and short form health survey-36 for cardiac patients
2. Does the improvement in health related quality of life persist after 3 month post pulmonary rehabilitation.

7.3 Please provide a summary of the present knowledge relevant to the research and make citation to any applicable scientific literature:

In patients with chronic lung and heart diseases, CP-R has important health benefits such as improvement in symptoms, exercise tolerance, and quality of life.(1) However, the effect of CP-R on sleep quality is controversial. Disturbed sleep is associated with, frequent exacerbations, increase in the severity of disease and increased mortality in COPD.(2) Sleep quality is a good predictor of quality of life in patients with stable COPD.(3) Increase in physical activity improves sleep in healthy individuals.(4) However, there has been little investigation into non-pharmacological methods to improve sleep quality in patients with COPD. It is also uncertain, how long the beneficial effects of pulmonary rehabilitation on sleep quality, if any, usually last. In an observational study, CP-R was associated with a statistically significant improvement in sleep quality.(1) Other researchers did not find any significant benefit of CP-R on quality of sleep.(5, 6) Due to lack of robust data, we sought to find the effect of CP-R on sleep quality.

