8.4 * Please specify in detail the methods and procedures that are involved in this research:

Methodology:

Study Population:

This study will collect prospective data from patients being referred to Metrohealth's Pulmonary rehabilitation center.

If this field is not completed your protocol will not be reviewed. Do not enter N/A. Please describe what methods and procedures will be involved in this research.

Data collection plan:

The study will use data from questionnaires filled by patients before and after completion of pulmonary rehabilitation. A 3-month follow up survey using the same questionnaires will be conducted. The questionnaires that will be used include Pittsburgh sleep quality index (PSQI), Epworth sleepiness scale (ESS), Berlin questionnaire, COPD assessment test, Short form health survey-36 (SF-36), hospital induced anxiety and depression scale (HADS) and insomnia severity index (ISI). The questionnaires will be sent to the patients either through MyChart messaging or direct mail with a memo cover-sheet explaining the research study and voluntary participation. The surveys will be available to the participants through MyChart for four weeks after being sent out to give them ample opportunity to participate. The survey will not pop up each time with MyChart login but patients who have not filled the questionnaires will get a weekly reminder to complete the questionnaires when they login to MyChart. However, if the patient declines to participate in the study, the survey will not pop up again and no reminder will be sent. Since the questionnaires are being used to track changes before and after pulmonary rehabilitation, the participants will not be able to take the survey more than once at each point (beginning, end and 3-months post completion of pulmonary rehabilitation). All patients regardless of contact method (via mail or MyChart) will be able to bring printed and filled questionnaires on Day 1 of pulmonary rehabilitation. However, if a MyChart user prefers to fill the questionnaires online through MyChart, s/he will be able to do so. Follow up surveys at the end of pulmonary rehabilitation and 3-months post-completion will be returned via mail or MyChart depending on whether patients have signed up for MyChart or not. For MyChart users, the questionnaires will remain

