This is also known as NIH Experimental Procedure section or Clinical Trial Procedure/Experimental Flow section. Do not just attach documents in response to this question you must do a study design summary for IRB Review.

8.7 Please attach study design/subject visit schedule here:

Name	Description
Study Design History	

If you have an electronic schedule of study visits and/or procedures please attach here.

View: 09-00 Inclusion/Exclusion Criteria

9.0 Inclusion/Exclusion Criteria:

9.1 What are the inclusion criteria? Put this information in bullet form:

Inclusion criteria:

- Age > 18 years
- Patient who are willing to participate in follow-up survey 3 months after completion of PR.
- Patients who complete rehabilitation for at least 8 weeks.

Please list inclusion criteria.

9.2 What are exclusion criteria? Put this information in bullet form:

Exclusion criteria:

- Not meeting inclusion criteria

Please list exclusion criteria.

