9.4 Will you exclude women and minorities, or persons under 21 from enrollment?

No

Check yes or no.

9.5 If yes, which groups are you excluding? Provide justification for your decision.

List groups to be excluded then provide justification.

9.6 Attach Documents:

Name Description
There are no items to display

If you are unable to fit your answers in the text boxes provided please attach as a word document.

View: 10-00 Risk/Benefits

10.0 Assessment of Risk I:

10.1 Identify and distinguish between those procedures that are standard versus those that are experimental. Include the frequency and duration of each activity and the total length of subject participation:

The questionnaires including Pittsburgh sleep quality index, Epworth sleepiness scale, Berlin questionnaire, Health related quality of life questionnaires (Short form health survey-36 (SF-36) for cardiac patients and COPD assessment test for COPD patients), and hospital anxiety and depression scale and insomnia severity index (ISI) will be used for research purpose.

Patient will be asked to fill the questionnaires at baseline (start of pulmonary rehab), at completion of pulmonary rehabilitation and 3 months after completion of pulmonary rehabilitation. It will take 40-45 minutes to complete the questionnaires/ surveys each time.

All the patients will complete standard pulmonary rehabilitation as prescribed by the physician.

10.2 Describe any therapeutic alternatives to the research that may exist. How are they different from those procedures that subjects would normally undergo? Patients may elect not to participate in the survey study.

10.3 What are the outcome variables and how will they be analyzed? What are the statistical and analytical methods that will be used? *Note this section can be copied from the NIH Grant Application or from the Statistical and Analytical Methods section of the industry trial protocol.*

We will analyze the data using SPSS and STATA. The primary outcome measure will be the change in individual Pittsburgh sleep quality index scores at the beginning, end and after 3-months of cardiac and pulmonary rehabilitation. We will also screen patients for sleep apnea prior to starting rehabilitation using Berlin questionnaire.

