10.14 What is the risk/benefit ratio of the research?

The benefits of pulmonary rehabilitation are well documented that there is short-term improvement in respiratory symptoms and quality of life. This research study would help in understanding the impact of pulmonary rehabilitation on sleep quality as well as long-term benefits of pulmonary rehabilitation. The research study will not impact the pulmonary rehabilitation protocol itself nor will it take away time from the rehabilitation program. This study will also screen patients for sleep apnea. There is minimal risk of compromise of patient data which would be expected with any research study with similar design. However, the benefits outweigh the risks associated with the study.

Discuss why the risks are reasonable in relation to the anticipated benefits.

10.15 Attach Documents:

Name	Description
There are no items to display	

Attach documents here.

View: 11-00 Study Participant Information I

11.0 Study Participant Information I:

11.1 How will the Principal Investigator assure he/she has access to a population that would allow recruitment of the required number of study participants (i.e. prep for research):

Pulmonary rehabilitation patients are within the scope of the PI's practice. Each pulmonary rehabilitation group has 5-10 participants. The program is usually 8 weeks long. 2 new groups start each week. Approximately 50% of the participants complete the rehabilitation program.

How does the PI know he/she has the required number of subjects?

11.2 For our study to have sufficient power, we need 27 patients.

Please give the total #of subjects to be enrolled at all sites and anticipated subjects to be enrolled at MHS.

Anticipated number of subjects (all sites): [enter a number]

Anticipated number of subjects to be enrolled at MHS: [enter a number]

80

Anticipated number of potential subjects to be approached: [enter a number]

80

11.3 If this is a multi-site study, how many sites will there be? [enter a number] How many total sites?

11.4 Subject Characteristics:

Subject Population Categories

Outpatients

Check all that apply

11.5 Subject Source:

Subject Source Characteristics

Subjects from the Practice of the Principal Investigator

Check all that apply

11.6 If "other" list above in either 11.4 or 11.5 please describe:

If applicable please describe.

View: 12-00 Study Participant Information II

12.0 Study Participant Information II:

12.1 Select age range of study participants:

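### Primary aim 3 (sleep impairment and a positive apnea screen) has no analysis in the protocol or SAP, and inclusion criterion 9.1 as written would restrict it to rehabilitation completers

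*SAP*

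**What the plan says.** Protocol 7.2 lists three primary aims: whether rehabilitation improves sleep quality, then "Does the improvement in sleep quality persist after 3 months", then "Is sleep impairment associated with positive screen for sleep apnea".

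The SAP is a single paragraph. Its primary outcome is PSQI change over three time points (start, end and 3 months later). For means it says "A paired-sample Student t-test will be used to compare means before and after the CP-R". For associations it says that Pearson's "product co-efficient (r) will be used to analyze association between changes in Pittsburgh sleep quality index, hospital anxiety and depression scale", and it continues the list with the COPD assessment test, Epworth scale and SF-36. It closes with one sample-size calculation: 27 pairs for a mean paired difference of 3 with SD 4.6, 90% power and type I error 0.05.

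Protocol 10.3 has nearly the same text plus one sentence that the SAP lacks: "We will also screen patients for sleep apnea prior to starting rehabilitation using Berlin questionnaire". It attaches no test to that sentence. The SAP mentions neither the Berlin questionnaire nor apnea.

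On population, one inclusion criterion in protocol 9.1 reads "Patients who complete rehabilitation for at least 8 weeks". Protocol 11.1 says "Approximately 50% of the participants complete the rehabilitation program". Under 12.5, patients consent by bringing their forms on Day 1, and 8.6 says that this consent covers the whole study. Protocol 13.3 plans to approach 80 patients.

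**The concern.** A primary aim should have a stated comparison, a stated measure on each side and a stated set of patients. Aim 3 has none of these. The SAP followed exactly would give no result for it, and any analysis added later would be chosen with the data in hand.

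The patient set is a separate problem. The Berlin and the baseline PSQI are both collected before or on the first day, so aim 3 is a cross-sectional question that can be answered for everyone who returns Day 1 forms. Criterion 9.1 makes completion of at least 8 weeks a condition of inclusion. Applied to aim 3, that would remove consenting patients because of something that happens after both measurements. The sample would be smaller, and the association would be estimated only in patients selected on finishing. If poor sleep or apnea risk is related to dropping out, the estimate could differ from the one in the referred population.

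**Working it through.** **1. The plan's own figure.** For a paired t-test, two-sided 0.05, the noncentrality is (difference / SD) × √n.

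- n = 27: (3 / 4.6) × √27 = 0.652 × 5.196 = 3.39 on 26 df; power 0.903.
- n = 26: noncentrality 3.33; power 0.892.

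So 27 is the smallest n that reaches 90%, and the stated figure reproduces. It sizes one within-patient contrast. Protocol 8.4 makes baseline versus end the natural one: "The study will use data from questionnaires filled by patients before and after completion of pulmonary rehabilitation".

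**2. Does any stated method reach aim 3?**

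| Method in SAP | What it compares | Reaches aim 3? |
|---|---|---|
| Paired t-test | The same patients before and after rehabilitation | No: aim 3 compares screen-positive with screen-negative patients |
| Pearson r | Changes in PSQI, HADS, CAT, ESS and SF-36 | No: Berlin is not in the list |
| Sample size | One paired difference | No: it is not a between-group calculation |

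The Pearson sentence also contains a stray reference to the beginning of rehabilitation. Even if that means baseline values, Berlin is still absent.

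**3. How many patients criterion 9.1 would remove.** From 13.3 and 11.1, 80 × 0.50 = 40 completers. Eighty is an upper limit for baseline forms, because it supposes that everyone approached takes part. The halving itself follows from the 50% completion rate, whatever the participation.

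**4. What that does to precision (illustration).** The documents give neither a between-patient SD for baseline PSQI nor the share who will screen positive. The result is therefore in SD units, with an assumed high-risk share of 30% to 50%. For a two-sample t-test, two-sided 0.05, with groups n₁ and n₂, the noncentrality is d × √(n₁n₂ / (n₁ + n₂)), where d is the difference in SD units. For 80% power it must be about 2.875 on 38 df and 2.837 on 78 df.

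| Patients | Split | √(n₁n₂/N) | Detectable d |
|---|---|---|---|
| 80 | 40/40 | 4.472 | 2.837 / 4.472 = 0.63 |
| 80 | 24/56 | 4.099 | 2.837 / 4.099 = 0.69 |
| 40 | 20/20 | 3.162 | 2.875 / 3.162 = 0.91 |
| 40 | 12/28 | 2.898 | 2.875 / 2.898 = 0.99 |

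Restricting to completers raises the detectable difference by a factor of about 1.43 (0.909 / 0.634), close to √2, as expected from halving the sample.

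**The case against.** **Criterion 9.1 may not have been meant for aim 3.** Forms go out before rehabilitation and come back on Day 1, when nobody can know who will complete. Protocol 13.3 treats non-completion as attrition from the 80 approached, and 16.16 has completion tracked by chart review. Read together, 9.1 was plausibly intended to define the before-after set. This stands as a reading of intent. A reader might infer that the investigators plan to drop Berlin data from non-completers, and no document says that. But 9.1 is worded as a condition of inclusion for the whole study, so the limit on its scope has to be written down.

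**Aim 2 is not in the same position.** A reader might infer that persistence also lacks any analysis. The documents do not support that: 3-month PSQI is part of the primary outcome, a paired t-test is the only test of means, and 14.1 and 16.14 ask whether benefits last. A paired comparison of 3 months with baseline is the ordinary way to fill the gap. What is missing is the name of the contrast.

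A reader might also fear contradictory answers if persistence were claimed from a non-significant end-to-3-month change. In a simulation with a true gain of 3, SD 4.6 for both changes from baseline, correlation 0.5 to 0.7 and 27 or 40 pairs, that rule and the 3-month-versus-baseline test disagree after a significant gain at the end. They do so in 34% to 41% of trials if half the gain is lost, but in only 6% to 10% if it is kept and 3% to 8% if it is all lost. The high figure is for one scenario, under a rule that no passage proposes.

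**Power for a 3-point difference in aim 3 would be borrowed.** The 3 and the 4.6 belong to a within-patient change, so they do not give a between-group power figure. Only the results in SD units are used here.

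**Conclusion.** The point holds for aim 3. It has no analysis in either document, which is plain from the text and needs no assumption. As worded, 9.1 would also limit any later analysis of it to completers, about half of those with baseline data, selected on an event after the measurements. The size shown, a detectable difference of 0.63–0.69 SD rising to 0.91–0.99 SD, is an illustration. It rests on all 80 patients taking part, 50% completion and a high-risk share of 30% to 50%.

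For aim 2 the gap is a lesser one of wording. The 27 pairs are correct for the single contrast that they address, and nothing here disputes them. The documents do not require aim 3 to lose its primary status or the 3-month test to depend on the first; both are the sponsor's choices.

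**What to change.** **Main change.**

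- Add to the SAP, and to protocol 10.3, a comparison of baseline PSQI between Berlin high-risk and low-risk patients, reported as a difference with its 95% CI, in all consenting patients who returned baseline questionnaires. State how the Berlin form is scored into the two groups.
- State in 9.1 that the 8-week completion criterion defines the before-after analysis set and does not apply to aim 3.

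**Lesser clarification.**

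- Name end minus baseline PSQI as the contrast that the 27 pairs power.
- Name 3 months minus baseline as the aim 2 contrast.
- Report the end-to-3-month change with a 95% CI, and do not read a non-significant change as persistence.

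**Cost.** A few sentences in the SAP and in protocol 9.1 and 10.3. No new questionnaires, visits or patients are needed, since the Day 1 forms are already planned and consent covers them. The one drawback is that aims 1 and 3 will use different sets of patients, which must be reported separately.
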